### 3.3. Treatment

#### 3.3.1. Investigational Therapy

Patients who have provided written informed consent will undergo screening procedures. Once eligibility is established patients will begin therapy with Pasireotide LAR 40 mg.

Pasireotide LAR 40 mg will be administered as intra-muscular (i.m.) intragluteal injections every 4 weeks. Uptitration will occur to Pasireotide LAR 60 mg after 6 months of therapy with Pasireotide LAR 40 mg if POMC level has not been suppressed and/or pituitary tumor shrinkage has not occurred. For patient receiving 40 mg dose down-titration to 20 mg is permitted for patients who do not tolerate 40 mg. For patients who are up-titrated to the 60 mg dose down-titration to 40 mg is permitted if tolerability issues occur on this higher dose.

Medication labels will comply with legal requirements and be printed in English. The storage conditions for study drug will be described on the medication label.

Should anti-diabetic treatment be needed during the study (see adverse events) this will be provided by the investigator according to standard clinical practice for diabetes care. The order of initiation of anti-diabetic therapy is expected to be, but is not prescribed as part of this protocol:

- Metformin at individual doses starting from 1000 mg/day to maximum dose according to the approved package insert and depending on the patient tolerability
- Sitagliptin 50 or 100 mg administered orally once a day

- Insulin administered s.c. according to package insert

### 3.3.2. Concomitant therapy

Chronic maintenance medications will continue on their current therapy during the course of the study. The patient will be told to notify the investigational site about any new medications he/she takes after the start of the study drug. Any changes in the dose of any medication the patient was taking prior to or during the study have to be notified as well. All medications (other than study drug) and significant non-drug therapies (including physical therapy and blood transfusions) administered during the study will be documented in the subject records.

The use of drugs that may stimulate GH secretion such as L-dopa or arginine is not permitted. In addition, the use of the drugs listed in the exclusion criteria is not permitted.

Limited published data indicate that somatostatin analogs might decrease the metabolic clearance of compounds known to be metabolized by cytochrome P450 enzymes, which may be due to the suppression of growth hormones. Since it cannot be excluded that pasireotide may have this effect, other drugs mainly metabolized by CYP3A4 and which have a low therapeutic index (e.g., quinidine, terfenadine) should therefore be used with caution. Consumption of fruits that may inhibit the CYP3A4 system (star fruit, papaya, pomegranate and grapefruit) will also be advised against during the study.

Somatostatin analogs have been associated with alterations in nutrient absorption, so pasireotide may have an effect on absorption of orally administered drugs. Concomitant administration with cyclosporine may decrease blood levels of cyclosporine and result in transplant rejection.

Patients receiving insulin, oral hypoglycemic agents, beta-blockers, calcium channel blockers, or agents to control fluid and electrolyte balance, may require dose adjustments of these therapeutic agents. Any anti-diabetic medications that the patient takes during the study will be listed in study-specific source documents. If oral contraception is used, the patient must have been practicing this method of birth control for at least three months prior to enrollment and must agree to continue the oral contraceptive throughout the course of the study and for 3 months after pasireotide LAR last dose.

#### Prohibited concomitant medications

The use of concomitant medication with a known risk of Torsades de Pointes (TdP) is prohibited. In case a patient needs to take medication with a known risk of TdP, it will require study drug discontinuation prior to starting the medication. Appendix 1 lists QT prolonging medications.

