#### 1.2.1.1 Clinical Experience

##### 1.2.1.1.1 Pasireotide LAR

Pasireotide LAR has been extensively investigated in the clinical development program for healthy volunteers and various patient populations. Completed studies and studies with completed interim analyses are shown in the INVESTIGATOR'S BROCHURE, V15, P. 44, Table 5-1.

Pasireotide LAR demonstrated favorable PK profile for extended release in healthy volunteers and patients. PK steady state was achieved following 3 monthly (q28d) intra-muscular (i.m.) injections of pasireotide LAR in a study with both acromegaly and carcinoid patients. PK exposures of trough concentrations were approximately dose-proportional. CL/F of the Pasireotide LAR formulation was comparable to CL/F of the s.c. formulation (4.3-9.0 L/h). T1/2 for the Pasireotide LAR formulation was approximately 16 days, suitable for monthly dosing. The relative bioavailability of the Pasireotide LAR formulation to the s.c. formulation was complete, ranging from 106% to 148%. PK exposures in acromegaly patients were comparable to those in healthy volunteers. PK exposures in carcinoid patients were 2-fold higher than in healthy volunteers.

The efficacy of pasireotide LAR in acromegaly patients is based on CSOM230C2305, the phase III study to assess the safety and efficacy of pasireotide LAR vs octreotide LAR in patients with active acromegaly. In this study, pasireotide LAR was shown to be significantly superior to octreotide LAR for the treatment of acromegaly in medically naïve patients in terms of biochemical control (GH < 2.5 µg/L and normalization of IGF-1 levels) (31.3% vs. 19.2%; p-value 0.007), providing higher response rate in both de novo patients and in patients with prior pituitary surgery (25.7% vs. 17.3% in de novo patients; 39.4% vs. 21.8% in postsurgical patients). Pasireotide LAR was as effective as octreotide LAR in reducing tumor volume, improving acromegaly symptoms and ring size, and quality of life (27).

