19. Sexually active males unless they use a condom during intercourse while taking drug and for 3 months following last dose of pasireotide and should not father a child in this period. A condom is required to be used also by vasectomized men in order to prevent delivery of the drug via seminal fluid.
20. Pregnant or nursing (lactating) women, where pregnancy is defined as the state of a female after conception and until the termination of gestation, confirmed by a positive urine pregnancy test
21. Women of child-bearing potential, defined as all women physiologically capable of becoming pregnant, unless they are using highly effective methods of contraception during dosing and 3 months following last dose of pasireotide. Highly effective contraception methods include:
  - Total abstinence (when this is in line with the preferred and usual lifestyle of the subject. Periodic abstinence (e.g., calendar, ovulation, symptothermal, post-ovulation methods) and withdrawal are not acceptable methods of contraception)
  - Female sterilization (have had surgical bilateral oophorectomy with or without hysterectomy) or tubal ligation at least six weeks before taking study treatment. In case of oophorectomy alone, only when the reproductive status of the woman has been confirmed by follow up hormone level assessment

- Male sterilization (at least 6 months prior to screening). For female subjects on the study the vasectomized male partner should be the sole partner for that subject
- Combination of any two of the following (a+b or a+c, or b+c):
  - a) Use of oral, injected or implanted hormonal methods of contraception or other forms of hormonal contraception that have comparable efficacy (failure rate <1%), for example hormone vaginal ring or transdermal hormone contraception.
  - b) Placement of an intrauterine device (IUD) or intrauterine system (IUS)
  - c) Barrier methods of contraception: Condom or Occlusive cap (diaphragm or cervical/vault caps) with spermicidal foam/gel/film/cream/vaginal suppository
- In case of use of oral contraception women should have been stable on the same pill for a minimum of 3 months before taking study treatment.

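### The torsade-drug rule asks only that pasireotide LAR be discontinued first and sets no interval after the last 4-weekly depot injection, so a compliant patient can still have the combined exposure

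*Combined protocol and SAP*

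**What the plan says.** Section 3.3.2, under Prohibited concomitant medications, forbids drugs with a known torsade risk. For a patient who needs one, the only condition is that "it will require study drug discontinuation prior to starting the medication". No time since the last injection is stated.

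The study drug is long-acting. Section 3.3.1 says "Pasireotide LAR 40 mg will be administered as intra-muscular (i.m.) intragluteal injections every 4 weeks", with 60 mg available after 6 months; it also says that "down-titration to 20 mg is permitted for patients who do not tolerate 40 mg". Section 1.2.1.1.1 reports that "T1/2 for the Pasireotide LAR formulation was approximately 16 days, suitable for monthly dosing".

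Elsewhere the protocol does allow for drug that remains after the last dose:

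- Exclusion criterion 19 requires sexually active men to "use a condom during intercourse while taking drug and for 3 months following last dose of pasireotide". It adds: "A condom is required to be used also by vasectomized men in order to prevent delivery of the drug via seminal fluid".
- Section 3.4.4 continues adverse event review for at least 8 weeks after the drug is stopped. For serious events it uses 8 weeks for LAR but 30 days for the subcutaneous form.

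**The concern.** A depot cannot be withdrawn once injected. The rule treats discontinuation as the step that separates the two drugs, but the dose already given keeps acting. A site can therefore follow the rule exactly and still give the combination it is meant to prevent.

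Section 1.2.1.1.1 lists QT prolongation among the adverse reactions to pasireotide LAR. Appendix 1 includes azithromycin, clarithromycin and erythromycin, which may be needed promptly and for a short time. That is the situation in which stopping the depot has had no time to change exposure.

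**Working it through.** **Is an interval given anywhere else?** These are the places where one might be expected:

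- Exclusion criterion 7 bars torsade-risk drugs at entry. It sets no post-dose interval.
- Section 3.3.2 (Concomitant therapy) requires patients to report new medications. No interval.
- Interruption or discontinuation of treatment: no interval.
- The QT rules under Special Monitoring for Adverse Events act on an abnormal ECG and postpone or stop pasireotide. No interval.
- Section 3.4.4 sets 8 weeks for event review and reporting, not for starting other drugs.
- Appendix 1 is a drug list only.

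The protocol states no washout figure, so there is none to reproduce.

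**Up to day 28, with no model.** Days are counted from the last injection. The next injection would be due on day 28. Until then, a patient who stops and one who continues have received the same doses and have the same exposure. As an illustration, a 7-day course (assumed length) ends by day 28 if it starts in the first 28 − 7 = 21 days, which is 21/28 = 75% of possible start days. For a 3-day course the figure is 25/28 = 89%, and for a 10-day course 18/28 = 64%.

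**After day 28, with assumptions.** The inputs from section 1.2.1.1.1 are the 16-day half-life, that "PK exposures of trough concentrations were approximately dose-proportional", and that "PK steady state was achieved following 3 monthly (q28d) intra-muscular (i.m.) injections of pasireotide LAR". Two assumptions are added: log-linear decline, and a half-life range of 14 to 18 days to show sensitivity.

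Let *h* be the half-life and *r* = 2^(−28/*h*) the fraction of a trough left after a further 28 days. This gives *r* = 0.250, 0.297 and 0.340 for *h* = 14, 16 and 18. As a check, 1 − *r*³ = 0.974 at *h* = 16, which agrees with steady state after 3 injections.

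Express each patient's day-28 level as the dose with the same steady-state trough:

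- steady state on 40 or 60 mg: 40 or 60 mg
- a single first 40 mg injection: 40(1 − *r*)
- a first 60 mg injection after steady state on 40 mg: 60(1 − *r*) + 40*r*

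The level falls to the steady-state trough of 20 mg, the lowest study dose, on day 28 + *h* × log2(equivalent / 20).

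| Patient | Equivalent at *h* = 16 | Day, *h* = 14 | Day, *h* = 16 | Day, *h* = 18 |
|---|---|---|---|---|
| Steady state, 40 mg | 40.0 mg | 42.0 | 44.0 | 46.0 |
| Steady state, 60 mg | 60.0 mg | 50.2 | 53.4 | 56.5 |
| Single first 40 mg | 28.1 mg | 36.2 | 35.9 | 35.2 |
| First 60 mg after steady 40 mg | 54.1 mg | 48.4 | 51.0 | 53.4 |

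**What remains at candidate intervals** (steady state, *h* = 16, range for 14 to 18 days in brackets):

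- Day 56 (8 weeks), dose × *r*: 11.9 mg-equivalent after 40 mg (10.0 to 13.6) and 17.8 after 60 mg (15.0 to 20.4).
- Day 91 (3 months), dose × 2^(−63/*h*): 2.6 after 40 mg (1.8 to 3.5) and 3.9 after 60 mg (2.7 to 5.3).

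**The case against.** The rule is first of all a prohibition. The quoted sentence covers only a patient who truly needs the drug, and it is silent on timing rather than permitting an immediate start. Discontinuation also has value for long-term drugs on the list, because no further depot is added. Screening removes patients with a long QTcF, low potassium or magnesium, or serious cardiac disease. New medications must be reported, and adverse events are reviewed for at least 8 weeks after stopping. An urgent antibiotic would be given anyway, so in that case the remedy comes down to a few ECGs. The 20 mg benchmark has no established link to QT, and 8 weeks is a choice, not a derived washout.

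Most of this is fair as a limit on weight. The event is rare, the crossing days describe exposure and not risk, and 8 weeks is pragmatic. None of it supplies an interval. Because the rule names discontinuation as its one condition, a reader can take that step as sufficient. The day-28 point needs none of the modelling.

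The text of section 3.4.1 and the Investigator's Brochure were not available for this review. Nothing is therefore claimed about which ECGs a discontinued patient receives, and guidance in the brochure cannot be ruled out.

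**Conclusion.** The concern holds, as a minor point. The rule does not secure the separation it is written for: exposure is unchanged up to day 28. Under log-linear decline and dose-proportional troughs it stays at or above the 20 mg steady-state trough until about day 44 (42 to 46) after steady-state 40 mg and day 53 (50 to 57) after steady-state 60 mg. Before steady state at the current dose the crossing comes earlier. The increase in QT risk cannot be calculated from the documents, and few if any of the 10 patients would be affected.

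**What to change.** Amend the rule in section 3.3.2 on these lines:

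- Torsade-risk drugs count as concomitant for at least 8 weeks after the last LAR injection. This matches the follow-up already used in section 3.4.4. Clinicians may lengthen it, for example towards the 3 months used for contraception; at an 18-day half-life the 60 mg crossing falls just after 8 weeks.
- Within that window, use an alternative without torsade risk or defer treatment where clinically possible.
- If the drug must start sooner, do not delay urgent treatment. Take an ECG at the start and another shortly after on treatment, repeated only if the course continues. A potassium and magnesium check would be a sensible option, since exclusion criterion 7 names both deficiencies.
- If QTcF exceeds 480 msec, obtain the cardiology review already described in the QT rules. Direct it at whether to continue the torsade-risk drug, because pasireotide has already been stopped.

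The cost is two or three sentences of wording and one to three extra ECGs in a rare patient, plus a blood test if the electrolyte option is taken. Endpoint, sample size and analysis are unaffected.

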#### Interruption or discontinuation of treatment

Patients who experience an enlargement of their pituitary tumor or any clinical signs consider to represent progression of the tumor while on Pasireotide LAR therapy will be withdrawn from the study by the investigator. Patients that experience severe or life-threatening hyperglycemia (diabetic ketoacidosis, hyperosmolar coma), develop jaundice, hepatitis or other primary hepatic dysfunction will be discontinued from the study. Patients who develop an allergic reaction to Pasireotide LAR® Depot will be discontinued. It will be documented whether or not each patient completed the clinical study. If for any patient either study treatment or observations were discontinued the reason will be recorded. Reasons that a patient may discontinue participation in a clinical study are considered to constitute one of the following:

1. adverse event(s)
2. abnormal laboratory value(s)
3. abnormal test procedure result(s)

4. subject's condition no longer requires study treatment
5. protocol violation
6. subject withdrew consent
7. lost to follow-up
8. administrative problems
9. death

Any patient who receives at least one dose of trial medication will be included in the safety analysis.

	V1	V2	V3	V4	V5	V6	V7	V8	V9	V10	V11	V12	V13	V14	V15
OGTT (75 gm)		X					X							X	
CBC (w/ WBC differential)	X			X			X			X				X	
Hepatic Function Panel (AST, ALT, Bilirubins, AlkPhos)	X			X			X			X				X	
Basic Metabolic Panel (Na, K, Cl, HCO 3 , BUN, Cr, Ca)	X			X			X			X				X	
Serum Cortisol	X	X	X	X	X	X	X	X	X	X	X	X	X	X	
Plasma POMC	X	X	X	X	X	X	X	X	X	X	X	X	X	X	
Plasma ACTH	X	X	X	X	X	X	X	X	X	X	X	X	X	X	
Thyroid Panel (Free T4, TSH)	X														
Coagulation (PT, PTT)	X						X							X	
Serum & Plasma Bank	X	X	X	X	X	X	X	X	X	X	X	X	X	X	
Urinalysis	X							X						X	
Urine Pregnancy	X														
24 Hr Urinary Free Cortisol and Creatinine	X														
Salivary Cortisol (late night)(x5)	X							X						X	
Pituitary MRI w/ contrast	X							X						X	
Gallbladder Ultrasound and reading	X													X	
12 Lead ECG and reading	X	X	X	X			X			X				X	

### 3.4.2. Safety assessments

Safety assessments will consist of monitoring and recording all adverse events and serious adverse events, as well as regular monitoring of blood chemistries, and the regular measurement of vital signs as well as physical examinations and EKGs. Laboratory evaluations include clinical chemistries including BUN, creatinine, electrolytes, serum glucose, liver function tests to be performed in the CUMC/NY Presbyterian Hospital clinical laboratory. Safety assessments will be ongoing throughout the study and be conducted by the Sponsor-Investigator. A follow up visit 8 weeks after the final study visit will be conducted for a safety follow up.

#### Adverse events

Information about all adverse events, whether volunteered by the subject, discovered by investigator questioning, or detected through physical examination, laboratory test or other means, will be collected and recorded in study-specific source documents and followed as appropriate. An adverse event is any undesirable sign, symptom or medical condition occurring after starting study drug (or therapy) even if the event is not considered to be related to study drug (or therapy). Study drug (or therapy) includes the drug (or therapy) under evaluation, and any reference or placebo drug (or therapy) given during any phase of the trial.

Medical conditions/diseases present before starting study treatment are only considered adverse events if they worsen or become more frequent after starting study treatment. Adverse events occurring before starting study treatment but after signing the informed consent form will be recorded in the subject records. Abnormal laboratory values or test results constitute adverse events only if they induce clinical signs or symptoms or require therapy, and will be recorded in study-specific Adverse Events source documents.

As far as possible, each adverse event will also be described by:

1. its duration (start and end dates),
2. the severity grade (mild, moderate, severe)
3. its relationship to the study drug (suspected / not suspected),
4. the action(s) taken and, as relevant, the outcome.

Guidelines for treatment of patients experiencing AEs (Per CTCAE V4.03)

Medication	Adverse event	Action
Pasireotide LAR i.m.	AE CTC grade $\leq$ 2	No drug adjustments

Medication	Adverse event	Action
	AE CTC grade $\geq 3$ and assessed as study drug related	
Reduce pasireotide LAR i.m. dose by 20 mg. If the AE improves to grade <math>\leq 2</math> before the next administration, increase dose back to the prior dose. If the dose is increased and the AE recurs at a grade <math>\geq 3</math>, the dose should be reduced back to 20 mg. Down-titration should proceed similarly if patients have been uptitrated to 60 mg per month with down-titrations proceeding from 40 mg and then to 20 mg as indicated. The patient should stay on this lower dose if clinical benefits are maintained.
 
If the AE does not improve to grade <math>\leq 2</math>, the dose is to be reduced further if clinical benefits are maintained. If the AE does not improve to grade <math>\leq 2</math> on the minimum study dose, the treatment should be stopped. The patient should be discontinued and followed up for safety.

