Safety and efficacy in humans is summarized in the Investigator's Brochure, version 15, section 5.2. Pasireotide LAR safety is based on studies in patients with Acromegaly, Investigator's Brochure, V15, section 5.2.1.1.3. Safety assessment was based on 491 acromegaly patients who received pasireotide (419 patients received pasireotide LAR and 72 received pasireotide s.c.) in Phase I, II and III studies. The safety profile of pasireotide LAR is consistent with the somatostatin analogs class, except for the higher degree and frequency of hyperglycemia seen with pasireotide LAR. In Study SOM230C2305, the mean duration of exposure to pasireotide LAR across core and extension phase was 75 weeks (N=178).

The most frequent ADRs reported for more than 15% in the pasireotide LAR or octreotide LAR arms core and extension phase were diarrhea (33.1% and 40.6%), cholelithiasis (30.9% and 36.7%), hyperglycemia (28.1% and 7.2%) and diabetes mellitus (19.7% and 3.9%), alopecia (15.7% and 14.4%) and abdominal pain (12.9% and 17.8). Common Toxicity Criteria (CTC) grade 3 or 4 ADRs reported for more than 2% of the patients in the pasireotide LAR and octreotide LAR arms were diabetes mellitus (4.5% and 0%), diarrhea (0.6% and 2.8%) and hyperglycemia (2.2% and 0.6%). ADRs reported in patients who crossed over to the other treatment arm in the Phase III study were similar to those reported in the core and extension.

In the Phase III Study SOM230C2402, The mean duration of exposure in the core phase of Study C2402 was 24 weeks for all treatment groups.

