## SPECIAL MONITORING FOR ADVERSE EVENTS

### QT

- **QT 480 msec < QTcF  $\leq$  500 msec**

If at any visit a 480 msec < QTcF  $\leq$  500 msec is observed for a first time for a patient at a given dose level, the following steps will be taken. A cardiology consultation will be sought as soon as practical but within 7 days of the initial finding of abnormal ECG and the cardiologist must re-evaluate the ECG. The study treatment will be postponed until a cardiologist has re-evaluated the ECG.

- If a QTcF > 480 msec is NOT confirmed, no further action needs to be taken.
- If a QTcF > 480 msec is confirmed, a cardiologist must perform a thorough examination (such as reviewing baseline ECG, concurrent medications and performing a cardiovascular examination, including at least a cardiac auscultation) to assess the patient for cardiovascular risk factors.
- If based upon the assessment by the cardiologist, the investigator considers that there is an acute cardiovascular safety risk and that the patient should not continue with study medication, the patient will be discontinued immediately (discontinuation criteria to be followed).
- If following the examination by the cardiologist, the investigator considers that there is no acute cardiovascular safety risk the patient can continue to receive study medication.

- **QTcF > 500msec**

If at any visit a QTcF > 500msec is observed, the following steps need to be taken:

- Triplicate ECGs, each 2-3 minutes apart, need to be taken approximately 1 hour after the initial ECG. The mean QTcF from the triplicate ECGs will be determined. If

the mean QTcF is > 500msec, the patient has to postpone study treatment until a cardiologist has re-evaluated the ECG. The re-evaluation needs to be done as soon as practical but within 7 days of the initial finding of abnormal ECG.

- If the cardiologist confirms a mean QTcF > 500msec, the patient has to be withdrawn from the study.
- Otherwise and if the cardiologist confirms that at least one ECG shows a QTcF > 480msec, the cardiac assessments described for a confirmed QTcF > 480msec need to be followed.

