### Hepatic Safety

- Patients who develop increased transaminase levels will be monitored with a second liver function evaluation to confirm the finding. If the finding is confirmed, the patient will be followed with weekly liver function monitoring (AST, ALT, bilirubin levels, Alkaline phosphatase) until values return to pre-treatment levels.
- If any of the criteria below are observed at any scheduled or unscheduled visit the sponsor will perform a follow up within **72 hours** of awareness of the abnormality:
  - ALT or AST > 3 x ULN and Total Bilirubin  $\geq$  2 x ULN
  - ALT or AST > 5 x ULN and  $\leq$  8 x ULN
  - ALT or AST > 8 x ULN
- Hepatic Safety Follow up:
  - Perform liver-directed medical history and physical examination (i.e. assess occupational hazards, concomitant medications including over-the-counter medications, inter-current illness, etc.)
  - Liver chemistry tests: ALT, AST, total bilirubin, (fractionate to direct/indirect bilirubin if total bilirubin is > 2.0 x ULN), Albumin, PT (INR), ALP, and GGT. These tests will be monitored every **3-4 days** until resolution or return to baseline status.
  - Perform hepatitis screen: anti-HAV, IgM (to confirm acute hepatitis A), HbsAg, Anti-HBc, anti-HCV (if positive, PCR viral load should be assessed), Anti-HEV, ANA antibodies, anti-smooth muscle anti-bodies, CMV and EBV
  - Perform abdominal ultrasound (liver and biliary tree)
- Patients may need to be discontinued if the abnormal liver function criteria are met upon LFT retesting or immediately discontinued without LFT retesting in the case of ALT or AST > 8 times the upper limit of normal. Progress reports of the event will be maintained until resolution or return to baseline status.
- If any of these criteria are met and deemed an AE by the investigator, the event will be recorded on in the subjects records as well as the adverse event log; if the event is deemed serious by the investigator, then an SAE will be reported (as described below in SAE reporting procedures). In addition, any clinically significant findings from the physical examination will be recorded in the subjects study records and adverse event log.

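### The adverse event rule for laboratory and test results does not count a finding because it led to withdrawal, so a symptom-free, untreated patient withdrawn for confirmed QTcF >500 ms need not appear as an adverse event

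*Combined protocol and SAP*

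**What the plan says.** Section 3.4.2 (Adverse events) opens with a broad definition: "An adverse event is any undesirable sign, symptom or medical condition occurring after starting study drug (or therapy". It then narrows this for laboratory and test findings: "Abnormal laboratory values or test results constitute adverse events only if they induce clinical signs or symptoms or require therapy". It also asks that each event be described by "the severity grade (mild, moderate, severe"), while the dose-action table in the same section is keyed to CTCAE v4.03 grades. That table's dose-reduction row applies to events of grade 3 or more "and assessed as study drug related".

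The special monitoring part of section 3.4.2 acts on numerical findings:

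- **QT:** "If the cardiologist confirms a mean QTcF > 500msec, the patient has to be withdrawn from the study". This subsection has no instruction to record an adverse event.
- **Hepatic Safety:** patients may need to be discontinued if the criteria are met on retesting, or "immediately discontinued without LFT retesting in the case of ALT or AST > 8 times the upper limit of normal". On recording it says: "If any of these criteria are met and deemed an AE by the investigator, the event will be recorded on in the subjects records". A serious adverse event report follows if the investigator deems the event serious.
- **Hyperglycemia:** intervention follows at FPG above 130 mg/dL or HbA1c of 6.5% or more.

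Section 3.3.2 (Interruption or discontinuation of treatment) lists nine reasons for leaving the study. Adverse events are the first; abnormal laboratory values and abnormal test procedure results are the second and third, listed separately.

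The Protocol Summary names ECG, laboratory evaluations and gallbladder ultrasound as safety assessments. The visit table schedules the ultrasound at V1 and V14. Section 4.1 specifies no tabulation of adverse events, ECG, liver tests or ultrasound. Its only items of that kind are glucose, insulin and HbA1c.

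**The concern.** QT prolongation, transaminase rises and gallstones are all looked for here by scheduled tests, and a test can find them in a patient who feels well. The recording rule asks whether the patient had symptoms or was treated. It does not ask whether the finding was serious enough to stop the drug. The most consequential finding in the QT rules, one that ends participation, can thus fall outside the adverse event count while a mild symptomatic complaint falls inside it.

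The adverse event listing is the natural source for the trial's safety statement, and section 4.1 plans no other table that would show ECG, liver or ultrasound findings. In an open-label study run by a sponsor-investigator, leaving the classification to case-by-case judgement also makes the count depend on who classifies the event.

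**Working it through.** The plan gives no figure on this point, so there is none to reproduce. The check sets the sections side by side and follows one patient through each.

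**QTcF above 500 ms**

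1. The triplicate ECGs have a mean QTcF above 500 ms, the cardiologist confirms it, and the patient is withdrawn (section 3.4.2, QT).
2. Assume no signs or symptoms and no therapy. Neither limb of the laboratory and test rule is met, and withdrawal is not a third limb.
3. The QT subsection does not say that an adverse event is recorded.
4. The third reason in section 3.3.2, an abnormal test procedure result, fits the case and is separate from the adverse event reason.
5. Section 4.1 has no ECG table.

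Result: one patient withdrawn for a drug-safety finding, and possibly no adverse event counted.

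**ALT or AST above 8 x ULN**

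1. Under the general rule, a symptom-free, untreated value is not an adverse event.
2. Under Hepatic Safety, the same value is logged if the investigator deems it an adverse event, with no criterion given.

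Result: two tests for one finding, and a count of 0 or 1 depending on judgement. The lower hepatic criteria are in the same position.

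**New gallstones at V14, symptom-free and untreated**

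1. Read as a test result, they are not an adverse event.
2. Read as a medical condition under the opening definition, they are.

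Result: ambiguous.

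**Hyperglycemia**

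Where the intervention at FPG above 130 mg/dL or HbA1c of 6.5% or more is drug therapy, the therapy limb is met and the event counts. Most actionable hyperglycemia is already covered.

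**Grading**

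The event description asks for three severity words, while the dose-action table needs a CTCAE grade. The first does not supply the second.

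**Size, with N = 10 (section 3.2)**

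- One uncounted patient: 1/10 = 10 percentage points.
- 0/10 reported: exact 95% interval 0 to 1 - 0.025^(1/10) = 0.308, that is 0 to 30.8%.
- 1/10 reported: exact 95% interval 0.3% to 44.5%, with lower limit 1 - 0.975^(1/10) = 0.0025.

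These figures show how much one classification matters. They do not estimate how often it will happen, because the documents give no rate for QTcF above 500 ms or ALT above 8 x ULN, and no share of findings that are symptom-free and untreated.

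**The case against.** The strongest reply is that the plan leaves room to count these events and loses no data. Much of that stands.

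- **Discretion exists.** An investigator may call either finding a medical condition, or treat it as medically significant under section 3.4.3. Section 3.4.4 has the sponsor-investigator review adverse events for seriousness when a laboratory value is received. Hepatic Safety has explicit adverse event and serious adverse event routes. A reader might infer that the rule shuts such findings out of serious adverse event reporting. It does not; it leaves entry to judgement.
- **ALT above 8 x ULN.** A reader might infer that every such patient is taken off treatment and goes uncounted. The Hepatic Safety sentence opens permissively, and logging is allowed. The QTcF case is the clear one.
- **Data are kept.** Discontinuation reasons, laboratory results and ECG records are retained (sections 3.3.2 and 5.2 and the QTcF appendix), and ten patients can be described one by one.
- **Gallstone rates.** Section 1.2.1.1.1 gives cholelithiasis in 9.5% over 24 weeks at 40 mg, and in 30.9% with a mean exposure of 75 weeks. In 10 patients that is 0.95 to 3.09 expected cases, and a chance of at least one of 1 - 0.905^10 = 63.1% to 1 - 0.691^10 = 97.5%. It is tempting to read these as the chance of a missed event. They are the chance of any reported case, in acromegaly patients, and the upper rate comes from longer exposure than here, where the last injection is at Week 44. The number uncounted could be none or all.
- **Comparability.** A reader might infer that the trial's rates cannot be set beside the background rates, which include QT prolongation and increased ALT. The documents do not state the adverse event rule those trials used, so this is not shown.
- **Scope.** The stated objectives are POMC and tumor volume, so safety counts are not the trial's formal question.

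What the reply does not remove is the conflict itself: the written rule, the separate discontinuation reasons and the silent QT subsection together allow a safety withdrawal with no adverse event.

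**Conclusion.** The concern holds as a defect in classification and counting. Followed as written, the plan does not require an adverse event to be recorded for a symptom-free, untreated patient withdrawn for confirmed mean QTcF above 500 ms. For the hepatic criteria the decision is the investigator's, under a test that differs from the general rule. For new silent gallstones at V14 the text supports either answer.

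Each uncounted patient is worth 10 percentage points in a trial of 10. The conclusion assumes that the finding causes no signs or symptoms and is not treated; a treated finding is an adverse event already. The number of patients affected cannot be derived from the documents. They do not support saying that these events are barred from the count, that the data are lost, or that a particular number will be missed.

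**What to change.** Amend the laboratory and test sentence in section 3.4.2 (Adverse events) so that an abnormality is also recorded as an adverse event, with its CTCAE v4.03 grade, when it:

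- meets an action criterion already in the QT or Hepatic Safety subsections, or
- leads to a dose hold, dose change or discontinuation.

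State that a new gallbladder finding at V14 compared with V1 is recorded. In Hepatic Safety, replace the investigator-judgement condition for logging with this definition. Make the discontinuation reasons in section 3.3.2 consistent with it.

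The amendment must say that it is for recording and counting only. Without that sentence, newly defined events of grade 3 or more judged drug-related would enter the dose-action table and overlap with the QT, hepatic and hyperglycemia rules. The sponsor must reconcile how that table and those rules apply to such events. No clinical threshold or dose rule is proposed here.

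The cost is a short amendment, a few more log entries and somewhat higher reported adverse event counts. No test or visit is added.
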